(ANC < $1.0 \times 10^9/L$, with a single temperature of $\geq 38.3^\circ C$ or a sustained temperature of $\geq 38^\circ C$ for more than one hour)	Omit dose until resolved, then ↓ 1 dose level
Thrombocytopenia	
Grade 1 (PLT < LLN - $75 \times 10^9/L$) Grade 2 (PLT < $75 - 50 \times 10^9/L$)	Maintain dose level
Grade 3 (PLT < $50-25 \times 10^9/L$)	
 Omit dose until resolved to ≤ Grade 1, then: 
 ● If resolved in ≤ 7 days, then maintain dose level ● If resolved in > 7 days, then ↓ 1 dose level
Grade 4 (PLT < $25 \times 10^9/L$)	Omit dose until resolved to ≤ Grade 1, then ↓ 1 dose level
Investigations (Renal)	
Serum creatinine	
< $2 \times ULN$	Maintain dose level
2 – 3 $\times ULN$	
 Omit dose until resolved to ≤ grade 1, then: 
 ● If resolved in ≤ 7 days, then maintain dose level ● If resolved in > 7 days, then ↓ 1 dose level
Grade 3 (> $3.0 - 6.0 \times ULN$)	Permanently discontinue patient from BYL719
Grade 4 (> $6.0 \times ULN$)	Permanently discontinue patient from BYL719
Investigations (Hepatic)	
Bilirubin	
(*for patients with Gilbert Syndrome these dose modifications apply to changes in direct bilirubin only)	
Grade 1 (> $ULN - 1.5 \times ULN$)	Maintain dose level with LFTs* monitored as per protocol
Grade 2 (> $1.5 - 3.0 \times ULN$) with ALT or AST $\leq 3.0 \times ULN$	
 Omit dose until resolved to ≤ Grade 1, then: 
 ● If resolved in ≤ 7 days, then maintain dose level ● If resolved in > 7 days, then ↓ 1 dose level
Grade 3 (> $3.0 - 10.0 \times ULN$) with ALT or AST $\leq 3.0 \times ULN$	
 Omit dose until resolved to ≤ Grade 1, then: 
 ● If resolved in ≤ 7 days, ↓ 1 dose level ● If resolved in > 7 days discontinue patient from BYL719
Grade 4 (> $10.0 \times ULN$)	Permanently discontinue patient from BYL719
AST or ALT and concurrent Bilirubin	
AST or ALT > $3.0 \times ULN$ and total bilirubin > $2.0 \times ULN$	Permanently discontinue BYL719

*LFTs include albumin, ALT, AST, total bilirubin (fractionated if total bilirubin > $2.0 \times ULN$), alkaline phosphatase (fractionated if alkaline phosphatase is grade 2 or higher) and GGT. For patients with

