Pneumonitis	
 In patients who have new or worsening respiratory symptoms or are suspected to have developed pneumonitis, interrupt PIQRAY immediately and evaluate the patient for pneumonitis. Permanently discontinue PIQRAY in all patients with confirmed pneumonitis.
Investigations (any other)	
Other adverse events	
Grade 1 or 2	Maintain dose level
Grade 3	Omit dose until resolved to \leq grade 1, then \downarrow 1 dose level
Grade 4	Omit dose and then discontinue from study drug treatment Omit dose for \geq grade 3 vomiting or grade 3 nausea only if the vomiting or nausea cannot be controlled with optimal antiemetic (as per local practice)

6 Study Procedures and Assessments

The study-specific assessments are detailed in this section. All on-study visit procedures are allowed a **window of ± 5 days** unless otherwise noted. Treatment or visit delays for public holidays or weather conditions do not constitute a protocol violation.

A written, signed, informed consent form (ICF) and a Health Insurance Portability and Accountability Act (HIPAA) authorization must be obtained before any study-specific assessments are initiated. A copy of the signed ICF will be given to the subject and a copy will be filed in the medical record. The original will be kept on file with the study records.

All patients who are consented will be registered in OnCore[®], the Banner University Medical Center Clinical Trial Management System (CTMS). The system is password protected and meets HIPAA requirements.

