10.3 Protocol Early Stopping Rules

10.3.1 Toxicity

A continuous monitoring rule for safety will be instituted, to guard against excess toxicity from pre-operative treatment with BYL719 at 350 mg po daily, the RP2D for this agent. All patients will be treated at the dose of BYL719 350 mg po daily. After enrollment of the 6th patient, we will continuously monitor the number of patients who discontinue BYL719 and come off study for BYL719-attributable toxicity. A qualifying toxicity must be at least possibly related to BYL719, as judged by the treating investigator, and fulfill one of the following definitions:

- Grade ≥ 3 non-hematologic toxicity, with the exception of asymptomatic electrolyte abnormalities manageable with repletion.
- Intolerable non-hematologic toxicities of any grade, which persist despite optimal medical management.
- Grade ≥ 3 thrombocytopenia or neutropenia.
- Any grade toxicity that results in a significant delay of surgery, defined as more than 42 days from the start of BYL719 protocol treatment.

If the posterior probability of $\geq 33\%$ toxicity rate exceeds 50% for patients having to discontinue window treatment due to qualifying toxicity, this would be considered unacceptable. The study would be placed on hold and would be referred to the UACC DSMB for evaluation of excess toxicity and recommendations for design change or study closure.

Table 8 below describes the number of toxicity events per number of treated patients required to trigger referral to the UACC DSMC. Table 8 also shows the posterior probability that the rate exceeds 33%, and the binomial probability associated with the decision for an assumed 33% discontinuation rate. The prior probability has a beta distributions with parameters $a = 1$ and $b = 9$, assumes a 10% mean with an approximate 80% mid-range of .0 to .22.

Table 8. Boundaries for the Excess Toxicity Rule

Subjects	Treatment-Related Discontinuations	PP($\pi > 33\%$)*	Pr($X \geq r p = .33$)
6	5	.629	.017
8	6	.685	.019
11	7	.673	.037
14	8	.664	.054
17	9	.657	.071
20	10	.650	.087

* π is the discontinuation rate. The minimum acceptable upper bound of a treatment-related discontinuation is 33%. PP($\pi > 33\%$) is the posterior probability that the discontinuation rate exceeds this 33% upper bound. This posterior probability of discontinuation is calculated from the prior distribution, the number of subjects treated and the observed number of treatment-related discontinuations.

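### Section 10.3.1 is inconsistent about which discontinuations feed Table 8, so some permanent stops required by Table 5 or section 5.3 may not count towards the toxicity boundary

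*Combined protocol and SAP*

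**What the plan says.** **The monitoring rule (section 10.3.1).** From the sixth patient on, "we will continuously monitor the number of patients who discontinue BYL719 and come off study for BYL719-attributable toxicity". The text then narrows the count: "A qualifying toxicity must be at least possibly related to BYL719, as judged by the treating investigator, and fulfill one of the following definitions". The four definitions are:

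1. Grade 3 or higher "non-hematologic toxicity, with the exception of asymptomatic electrolyte abnormalities manageable with repletion".
2. "Intolerable non-hematologic toxicities of any grade, which persist despite optimal medical management".
3. Grade 3 or higher "thrombocytopenia or neutropenia".
4. Toxicity of any grade that delays surgery to more than 42 days after the start of BYL719.

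The study is put on hold and referred for review if the posterior probability that the discontinuation rate is at least 33% exceeds 50%. In the text, that rate refers to stops due to qualifying toxicity. The Table 8 column heading and footnote describe the count as treatment-related discontinuations, with no mention of qualifying.

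**The mandatory stops (section 5.3 and Table 5 in section 5.6).** Confirmed pneumonitis: "Permanently discontinue PIQRAY in all patients with confirmed pneumonitis". The row headed "AST or ALT and concurrent Bilirubin" requires a permanent stop when AST or ALT is above 3 x ULN and total bilirubin is above 2 x ULN. A second QTcF occurrence also requires one, and an occurrence can be either QTcF above 500 ms or a change of more than 60 ms from baseline. For other Grade 4 events the instruction is "Omit dose and then discontinue from study drug treatment", and section 5.3 makes Grade 4 events in general a permanent stop unless otherwise specified.

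**The concern.** The rule is meant to monitor how often the drug has to be stopped for its toxicity before potentially curative surgery. One would expect a stop that the protocol itself makes permanent, and that the investigator considers at least possibly related, to be in the numerator. None of the four definitions says so, and some mandated stops can fall between them.

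The table and its footnote, read on their own, would include those patients; the paragraph above them would not. Two people tallying the same patients could therefore report different counts to the monitoring board. With 6 to 20 patients, one count is enough to decide whether the study is referred.

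**Working it through.** **Step 1. Set the mandatory stops against the four definitions.** Each event is taken as at least possibly related to BYL719.

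| Permanent stop | Def. 1: Grade 3+ non-haematologic | Def. 2: intolerable and persistent, non-haematologic | Def. 3: Grade 3+ platelets or neutrophils | Def. 4: surgery beyond 42 days |
|---|---|---|---|---|
| Confirmed pneumonitis, Grade 1-2 | No | Only if so judged | No | Only if delayed |
| AST/ALT above 3 to 5 x ULN with bilirubin above 2 to 3 x ULN | No: each is Grade 2 on Table 5's bands (above 3.0 to 5.0, and above 1.5 to 3.0) | Only if so judged | No | Only if delayed |
| Second QTcF change above 60 ms, QTcF not above 500 ms | Not on Table 5's labelling, which attaches Grade 3 and 4 to the level above 500 ms | Only if so judged | No | Only if delayed |
| Grade 4 haematologic event other than platelets or neutrophils (e.g. anaemia) | No | No: limited to non-haematologic | No | Only if delayed |

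Each row has a route by which the stop is not counted, and each also has at least one route by which it is.

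**Step 2. Reproduce Table 8.** Inputs from 10.3.1: prior Beta(1, 9), cut-off 0.33, limit 50%. With r stops among n patients the posterior is Beta(1 + r, 9 + n − r), and PP is its upper tail at 0.33. For 5 of 6, Beta(6, 10) gives .629. All six posteriors agree with the table, and so do all six binomial tails at p = .33 (.017, .019, .037, .054, .071, .087).

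**Step 3. Leave one stop out of the count.** The posterior becomes Beta(r, 10 + n − r).

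| n | Boundary r | PP at r (as in Table 8) | PP at r − 1 |
|---|---|---|---|
| 6 | 5 | .629 | .415 |
| 8 | 6 | .685 | .489 |
| 11 | 7 | .673 | .492 |
| 14 | 8 | .664 | .494 |
| 17 | 9 | .657 | .496 |
| 20 | 10 | .650 | .498 |

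Every value in the last column is below .50, so no referral follows.

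**Step 4. Illustrate the effect on the chance of a hold.** If the true rate of drug-related stops is p and a share f is not counted, the counted rate is p(1 − f). Exact recursion over patients 1 to 20 gives the chance of reaching the boundary. With a check after every patient from the sixth, the smallest r with PP above .50 is 5 at n = 6-7, 6 at 8-10, 7 at 11-13, 8 at 14-16, 9 at 17-19 and 10 at 20. The documents give no value for f or for the true rate; both are assumed.

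| True rate | Look schedule | f = 0 | f = 2% | f = 10% | f = 20% |
|---|---|---|---|---|---|
| 33% | every patient | .19 | .18 | .12 | .07 |
| 33% | six Table 8 rows | .12 | .11 | .07 | .04 |
| 50% | every patient | .73 | .70 | .57 | .40 |
| 50% | six Table 8 rows | .63 | .60 | .46 | .30 |

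**The case against.** A reader might infer that these toxicities never count. The documents do not support that. Non-haematologic events count at Grade 3 or higher, at any grade if intolerable and persistent, and at any grade if surgery is delayed beyond 42 days. Section 6.2.1 has the treating investigator document tolerability for every Grade 2 event, and nothing says that a laboratory or imaging finding can never be judged intolerable. Table 5's pneumonitis row begins from respiratory symptoms or clinical suspicion, so a silent finding is not the only case it covers.

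A reader might also infer that enrolment could continue after the plan's 50% limit has been passed. Under the text, that limit is defined on qualifying toxicity, so an uncounted stop does not breach it. The Table 8 wording can be read as shorthand for the paragraph above it.

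The size is also open to challenge. The smallest count that crosses a threshold will always fail when reduced by one, so Step 3 says nothing about how likely this is. The schedule suggests that laboratory-driven cases may be few: weekly visits require fasting glucose, adverse event assessment and medication review, the full blood panel is repeated once within 5 days before surgery, and Table 6.1 lists the EKG at baseline only.

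Other safeguards exist. Pneumonitis of any grade is recorded (section 8.2), the board reviews serious and non-serious events monthly (section 9.4), and the study can be suspended for unacceptable risk (section 11.7). A Table 8 crossing itself leads to a hold and referral, not automatic closure.

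All of this limits the point but does not remove it. The text and the table still describe different counts, and none of these safeguards says which one is used.

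**Conclusion.** The point holds as an inconsistency to be reconciled. Section 10.3.1 gives two descriptions of the numerator, and under the narrower one, four kinds of mandated permanent stop can go uncounted in the circumstances set out in Step 1. Where that happens to one patient at a Table 8 boundary, the posterior falls to between .415 and .498 and the referral that the table's wording would trigger does not occur. This rests only on the plan's prior and cut-off.

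The hold probabilities in Step 4 are illustrations that depend on assumed shares, an assumed true rate and the look schedule; they are not estimates of lost protection.

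Three things should not be read into this. No Table 8 figure is wrong. Nothing here bears on whether any Table 5 stopping criterion is the right one. And Grade 4 electrolyte abnormalities are not part of the point: 10.3.1 exempts asymptomatic, repletable electrolyte changes explicitly, which is the sponsor's choice.

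**What to change.** Reconcile the text of 10.3.1, the Table 8 column and footnote, and Table 5 with section 5.3. The simplest way is to add one qualifying definition to 10.3.1: any discontinuation at least possibly related to BYL719, whatever the grade, that section 5.3 or Table 5 requires to be permanent. State whether the existing electrolyte exemption still applies to such stops; that is for the sponsor to decide. If the narrower count is intended, correct the Table 8 column and footnote instead, so that they refer to qualifying discontinuations only.

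The change needs one sentence by amendment. The boundaries, posteriors and binomial tails in Table 8 stay as they are, and no clinical management rule changes. The downside of the wider count is a somewhat higher chance of a hold. At a true 33% rate with a check after every patient, it goes from .12 to .19 if 10% of stops would otherwise be uncounted (an assumed share). The .19 is what the rule gives when every treatment-related stop counts, as the Table 8 column describes.

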6.1 Screening Period & Pre-treatment Procedures

6.1.1 Screening Evaluations

Screening assessments must be performed within 28 days prior to the first dose of investigational product, unless otherwise specified. Any results falling outside of the reference

ranges may be repeated at the discretion of the investigator.

Note that all these procedures, with the exception of MUGA, are standard of care procedures for a patient with HNSCC.

Required screening evaluations include:

- Medical history assessment within 8 weeks prior to study registration.
- Physical examination, to include surgical and medical evaluation, within 8 weeks prior to study registration.
 - This is to include a careful description of the location and extent of the primary lesion and nodal spread. Fiberoptic nasopharyngoscopy/laryngoscopy is recommended, unless fiberoptic exam is deemed unnecessary by the treating surgeon. Examination under anesthesia (EUA) is recommended, unless deemed unnecessary by the treating physician.
- Vital signs, weight, height within 8 weeks prior to study registration
- ECOG Performance Status within 8 weeks prior to study registration
- Documentation of concomitant medications within 4 weeks prior to first dose of drug.
 - Note: All medications taken within 28 days prior to first dose must be documented, including blood transfusions.
- Laboratory studies including the following:
 - CBC with differential (to include total white blood cell count, absolute neutrophil count, hemoglobin, hematocrit and platelets),
 - Serum chemistries (to include sodium, potassium, chloride, carbon dioxide, BUN, creatinine, fasting glucose, magnesium, and calcium),
 - Liver function tests (LFTs; to include total bilirubin, AST, ALT, total protein, albumin and alkaline phosphatase),
 - Fasting amylase and lipase,
 - Coagulation studies (PT/INR and PTT) and
 - HbA1c.
- Negative serum pregnancy test within 4 weeks of study registration in WOCBP.

Note: the clinical research coordinator or treating investigator will document an additional negative serum or urine pregnancy test within 72 hours of starting BYL719 treatment.

- Cross-sectional radiologic evaluation within 6 weeks of study registration (within 4 weeks is preferred).
 - The minimum cross-sectional evaluation is a diagnostic, contrasted computed tomography (CT) scan of the neck.
 - PET/CT is the preferred modality, **provided it includes a diagnostic, contrasted CT scan of the neck** – however is not mandatory.
 - For patients with severe allergy to iodinated contrast dye despite premedication, or in the case of physician preference, neck MRI may be substituted.
- EKG. The standard of care EKG performed for pre-surgical evaluation should be used. EKGs performed within 12 weeks prior to study registration may be substituted, provided the patient has not experienced an interval cardiac event.
- Cardiac Multi Gated Acquisition (MUGA) or echocardiogram for determination of ejection fraction. MUGA or echocardiogram performed within 365 days prior to study registration may be substituted provided that the patient has not experienced an interval cardiac event.
- Confirmation of positive p16 status

6.1.2 Registration

- Questions regarding the eligibility of subjects must be directed to [name].
- After eligibility has been confirmed, registration will be submitted to the University of Arizona Cancer Center using the eligibility checklist. The following source documents must be submitted with the eligibility checklist.
 - Signed consent page with subject ID added, and PHI redacted
- “Registration” is defined as the day [name] signs the Eligibility Checklist confirming that the subject is eligible to start the study drug.

6.1.3 Mandatory Baseline Procedures Occurring Day -21 to -1

These procedures must occur prior to the initial dose of study drug. They can occur any time after the subject signs informed consent.

These Procedures are Mandatory.

- **Baseline, pre-treatment tumor biopsy**
 - Note that a research biopsy of the primary tumor or malignant lymph node for biomarker studies is a condition for enrollment unless sufficient tissue is available to be repurposed for use in this trial.
 - The biopsy will be performed per standard-of-care procedure in the surgeon’s outpatient office, or during the standard of care examination under anesthesia (EUA), as preferred by the surgeon.
 - The tissue can be obtained during the standard-of-care surgical/medical evaluation of the extent of primary lesion and nodal spread.
 - **NOTE:** Patients who have had research tissue procured under an omnibus tissue consent, who are determined to have sufficient fresh-frozen and paraffin tissue for biomarker analysis according to the PI, may substitute the archived tissue and do not need to undergo baseline research biopsy. Such tissue must have been obtained within 16 weeks prior to registration, provided no interval anti-neoplastic therapy was given.
 - Collection and preparation of tissue for biomarker analysis will be processed according to procedures described in the Laboratory Manual.
- **Baseline research blood collection**
 - For logistical purposes, research labs may be drawn simultaneous with blood labs required for standard clinical management.
 - Blood for biomarker analysis will be collected and processed according to procedures described in the Laboratory Manual.

6.2 Treatment Period

6.2.1 Day 1 Study Visit

- BYL719 will be dispensed. The BYL719 tablets are provided in 200 mg and 50 mg tablets.
- Study diary will be provided and explained (see Appendix 6)
- Adverse event assessment (and reporting of SAEs) will begin upon the first dose of study drug.
 - Prior to the first dose, active diagnosis and conditions will be considered medical history
 - For all grade 2 adverse events, treating investigator's determination of tolerable or intolerable must be documented for determination of AEs to be entered into the AE CRF
- Concomitant medication assessment (medications, herbal medications, and food or vitamin supplements taken within 28 days prior to Day 1 must be documented)

6.2.2 Study Drug Treatment - Days 1-21 and 22 (+/- 3 days)

NOTE: BYL719 treatment is planned for 10-21 days, however, may be administered up to 28 days if required for logistical/scheduling purposes.

- BYL719 will be administered at 350 mg orally once daily. This is one 200 mg tablet and three 50 mg tablets.
- The last dose of BYL719 will be taken on the day prior to surgical resection. The interval between the last dose of BYL719 and surgery will be approximately 24 hours (+/- 8 hours).
- If surgery is delayed, BYL719 may be continued until the day prior to surgery, for a maximum of 28 days. If this is the case, additional drug may be dispensed at Day 22.
- Subjects will be asked to indicate on a drug diary (see [Appendix 6](#)) when doses of BYL719 are taken in order to monitor for compliance. Subjects may also use the drug diary for notations on side effects and other treatment related events.

6.2.3 Day 8, 15, and 22 (+/- 3 days) if patient is on BYL719 treatment

- Weekly fasting plasma glucose
- Adverse event assessment.
- Concomitant medication review.

6.2.4 Day 9-29 (inclusive of day of surgery)

During treatment, pre-surgical

Ideally, subjects will have the surgery on day 22 or later. All efforts should be made to schedule these evaluations on **the day prior to or the day of surgery**, however a 5-day window is provided for logistical purposes, except for subjects with surgery on day 11 through 14. Subjects with scheduled surgery on day 11 through 14 should not have these procedures earlier than day 9. Subjects will continue to take BYL719 until the day prior to planned surgery. The interval

between the last dose of BYL719 and surgery will be approximately 24 hours (+/- 8 hours).

Compliance as evidenced by pill count and patient drug diary will be assessed when the subjects return the bottles and any leftover pills. This may happen after their surgery at the first follow-up visit if they do not have a clinic visit the day before surgery.

- *History and Physical Examination (During treatment, Pre-operative):* Subjects will be evaluated by history and physical examination by the treating physician prior to planned surgery (including vital signs, weight, performance status). This visit will also include adverse event assessment and compliance assessment as evidenced by pill count and patient drug diary. For logistical convenience, this visit may be scheduled in conjunction with blood collection and imaging as specified below.

NOTE: If surgery is unexpectedly delayed, subjects will continue to take BYL719, and this pre-operative history and physical examination does not need to be repeated.

- *Clinical and Research Blood Collection:* Subjects will undergo clinical labs including
 - CBC with differential,
 - serum chemistries including fasting glucose,
 - LFTs, and
 - coagulation studies prior to planned surgery.

Research blood will be drawn simultaneously with these standard pre-operative labs.

NOTE: If surgery is delayed, subjects will continue to take BYL719 and the clinical blood tests do not need to be repeated, but the research blood may be redrawn if the delay causes the research blood draw to be outside of the 5-day window prior to surgery.

- *Cross-sectional Imaging for Tumor Measurements (Research):* Subjects will undergo a repeat diagnostic CT scan of the neck with contrast prior to planned surgery as a part of the study. For patients with severe allergy to iodinated contrast dye despite premedication, or in the case of physician preference, neck MRI may be substituted.
NOTE: If surgery is delayed, subjects will continue to take BYL719, and this pre-operative imaging does not need to be repeated.

NOTE: in the event that a patient lacks a CT-measurable primary tumor or metastatic lymph node, measurable disease may be established by caliper measurement of an oropharyngeal tumor (≥ 1 centimeter). In this case, caliper measurement should be repeated and documented within 5 days prior to planned surgery, as a substitute for cross-sectional imaging.

